	
4. Patient has received prior treatment with anthracyclines at cumulative doses of 450 mg/m² or more for doxorubicin or 900 mg/m² or more for epirubicin.5. Patient with a known hypersensitivity to any of the excipients of ribociclib, mTOR inhibitors, e.g. sirolimus (rapamycin), or exemestane.6. Previous treatment with mTOR inhibitors7. Previous treatment with exemestane for advanced disease (except patients who received ≤28 days of exemestane for advanced breast cancer)8. Disease progression on more than one CDK 4/6 inhibitor, or have progressed more than once on the same CDK 4/6 inhibitor.9. Patient is concurrently using other anti-cancer therapy. All anti-cancer therapy must be discontinued at least 7 days prior to study treatment (C1D1). Drugs with overlapping toxicities with either everolimus or ribociclib must also be discontinued at least 7 days prior to C1D1. All AEs related to prior treatment should have resolved to CTCAE version 4.03 Grade ≤1 prior to study treatment (including any CDK 4/6 inhibitor)."10. Patient has had major surgery within 14 days prior to starting study drug or has not recovered from major side effects due to surgery.11. Patients with Child Pugh score B or C.12. Active, bleeding diathesis, or on oral anti-vitamin K medication (except low dose warfarin, LMWH and acetylsalicylic acid or equivalent, as long as the INR is ≤2.5 while on anti-coagulant). Fondaparinux is allowed.13. Radiotherapy < 2 weeks prior to starting study treatment. Patients must have recovered from radiotherapy toxicities prior to starting study treatment, and recovered to grade 1 or better from related side effects of such therapy (with the exception of alopecia). Radiotherapy is not allowed at target site following screening.14. Another malignancy within 3 years prior to starting study treatment, with the exception of adequately treated in-situ carcinoma of the cervix, uteri, basal or squamous cell skin carcinoma.15. Patients with central nervous system (CNS) involvement unless they are at least 4 weeks out from prior therapy completion (including radiation and/or surgery) to starting the study treatment.16. Patient has impairment of gastrointestinal (GI) function or GI disease that may significantly alter the absorption of the study drugs (e.g., ulcerative diseases, uncontrolled nausea, vomiting, diarrhea, malabsorption syndrome, or small bowel resection).17. Patient has a known history of HIV infection (testing not mandatory)
--	---

	
18. Patient has any other concurrent severe and/or uncontrolled medical condition that would, in the investigator's judgment, cause unacceptable safety risks, contraindicate patient's participation in the clinical study or compromise compliance with the protocol such as:
 
• chronic pancreatitis• active untreated or uncontrolled fungal, bacterial or viral infections, sepsis etc.• Uncontrolled diabetes as defined by fasting serum glucose $>1.5 \times \text{ULN}$• Acute and chronic, active infectious disorders including viral and nonmalignant medical illnesses that are uncontrolled or whose control may be jeopardized by the complications of this study therapy 
19. Fasting serum cholesterol $>300 \text{ mg/dl}$ or 7.75 mmol/L and fasting triglycerides $>2.5 \times \text{ULN}$. In case one or both of these thresholds are exceeded, the patient can only be included after initiation of statin therapy and when the above mentioned values have been achieved.
 
20. Significant symptomatic deterioration of lung function. If clinically indicated, pulmonary function tests including measures of predicted lung volumes, DLco, O₂ saturation at rest on room air should be considered to exclude restrictive pulmonary disease, pneumonitis or pulmonary infiltrates.
 
• Clinically significant, uncontrolled heart disease and/or cardiac repolarization abnormality including any of the following:• History of angina pectoris, symptomatic pericarditis, coronary artery bypass graft (CABG) or myocardial infarction within 6 months prior to study entry• Documented cardiomyopathy• Left Ventricular Ejection Fraction (LVEF) $<50\%$ as determined by Multiple Gated acquisition (MUGA) scan or echocardiogram (ECHO) detected during screening• History of cardiac failure or significant/symptomatic bradycardia Long QT syndrome or family history of idiopathic sudden death or congenital long QT syndrome or any of the following:• Known risk to prolong the QT interval or induce Torsade's de Pointes.• Uncorrected hypomagnesemia or hypokalemia• Systolic Blood Pressure (SBP) $>160 \text{ mmHg}$ or $<90 \text{ mmHg}$• Bradycardia (heart rate <50 at rest), by ECG or pulse.• On screening, inability to determine the QTcF interval on the ECG (i.e.: unreadable or not interpretable) or
--	--

	
QTcF >450 msec for men and >470 msec for women (using Frederica's correction). All as determined by screening ECG (based on a mean of 3 ECGs).
 
21. Patient is currently receiving any of the following substances and cannot be discontinued 7 days prior to Cycle 1 Day 1:
 
 • That have a known risk to prolong the QT interval or induce Torsade's de Pointes. • Known strong inducers or inhibitors of CYP3A4/5, including grapefruit, grapefruit hybrids, pummelos, star-fruit, and Seville oranges. • Medications that have a narrow therapeutic window and are predominantly metabolized through CYP3A4/5. • Herbal preparations/medications, (except for vitamins). 
22. Not able to understand and to comply with study instructions and requirements.
 
23. Pregnant or nursing (lactating) women, where pregnancy is defined as the state of a female after conception and until the termination of gestation, confirmed by a positive hCG laboratory test.
 
24. Sexually active males unless they use a condom during intercourse while taking drug and for 21 days after stopping medication and should not father a child in this period. A condom is required to be used also by vasectomized men in order to prevent delivery of the drug via seminal fluid.

Safety Assessments	
 • Incidence of Dose Limiting Toxicities (DLTs) in Cycle 1 (Phase I only) • Adverse Events (AEs), serious AE (SAEs), changes in hematology and chemistry values, vital signs, electrocardiograms (ECGs), dose interruptions, reductions and dose intensity
Efficacy Assessments	
CT/ MRI every 8 weeks for the first 12 months, then every 12 weeks thereafter until disease progression, death, withdrawal of consent, loss to follow-up, or subject/guardian decision.
 
 • Brain CT or MRI as clinically indicated. • Whole body bone scan at screening and as clinical indicated • Bone x-ray, CT or MRI (if bone lesion at screening) every 8 weeks for the first 12 months and then every 12 weeks thereafter until disease progression • Skin color photography (if skin lesions at screening) every 8 weeks during the first 12 months and then every 12 weeks thereafter.

	
• CT/ MRI for any disease outside of the chest, abdomen, pelvis (if lesion identified at baseline) every 8 weeks for the first 12 months and then every 12 weeks thereafter.• Survival status
Other Assessments	
Pharmacokinetic: Ribociclib, everolimus and exemestane pharmacokinetic (PK) evaluations. PK parameters, including but not limited to AUC_{0-6hrs}, C_{max}, C_{trough}.
 
Investigational and reference therapy	The investigational or study drug refers to ribociclib. Investigational treatment/arm refers to the triple combination of ribociclib + everolimus + exemestane (R-E-E).
IDMC and SSC	An Independent Data Monitoring Committee (IDMC) will be constituted. A Study Steering Committee (SSC) will also be constituted for overseeing the clinical trial
Dose, regimen	Every 28 days will be considered one cycle. Everolimus, exemestane and ribociclib will be administered daily.
Statistical methods	
Phase I:
 
The primary purpose of the Phase I is to estimate the MTD(s) and/or identify the RP2D of the combination treatment of ribociclib+ everolimus + exemestane when dosed continuously in adult men and postmenopausal women with HR+ HER2-negative advanced breast cancer resistant to the non-steroidal aromatase inhibitors (letrozole or anastrozole), fulvestrant or tamoxifen. The corresponding primary endpoint is the incidence of DLTs in the first cycle.
 
A patient is considered to have met the minimum exposure requirement if having received at least 75% of the planned combination doses for all compounds administered together (in the same day) for one cycle. The length of a cycle is 28 days.
 
Phase II:
 
Open label, Phase II trial will evaluate the anti-tumor activity of exemestane, everolimus and ribociclib triplet. This part of the study will be continued after the MTD/RP2D is determined in the Phase I.
 

	
A minimum of approximately 60 evaluable patients (30 per group (group 1, and group 2) are required for Phase II of this study to evaluate clinical benefit rate at 24 weeks.
 
The sample size is based on an exact test for single proportion to test the null hypothesis $H_0: p \leq 0.10$, where p is the clinical benefit rate in 24 weeks. If the true rate is $p \geq 30\%$, then with one-sided alpha level of 0.05% and a power of 80%, a minimum of approximately 30 evaluable patients for each group are required for the study. Including dropout rate of 10%, to get at least 30 evaluable patients, a total of approximately 33 patients for each group (group 1 and group 2) will be enrolled.
 
If 8 or more patients show clinical benefit at 24 weeks then the null hypothesis will be rejected and significant clinical benefit will be demonstrated. (See Section 10)
 
Details of the statistical analysis and data reporting will be provided in the RAP.

--	---

1 Background

[figure not shown]

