Study design	
Phase I:
 
A Phase I dose escalation (cohort A and B) and dose de-escalation (cohort C) will be initiated to ensure the safety and tolerability of daily dosing of ribociclib + everolimus + exemestane in patients with HR+, HER2-negative advanced/metastatic breast cancer. Once the recommended Phase II dose is confirmed and safety and tolerability are established, the trial will commence into a Phase II study.
 
Phase II:
 
This portion of the trial will be an open label, Phase II study to evaluate the antitumor activity of the ribociclib + everolimus + exemestane combination in patients that have progressed on CDK4/6 inhibitor based therapy.
 
Patients with advanced/metastatic HR+, HER2-negative, breast cancer will receive one of two RP2D determined by Phase 1, both Group 1 and Group 2.. All subjects that participate in Phase 2 must have progressed on a CDK 4/6 inhibitor. Prior CDK 4/6 inhibitor will be defined as disease progression while on, or within 30 days of discontinuing any CDK 4/6 inhibitor therapy (i.e. palbociclib, ribociclib, or abemaciclib).
 
Dose adjustment (reduction, interruption or dose re-escalation) according to safety findings will be allowed. Safety reviews by an Independent Data Monitoring Committee (IDMC) will be performed. Tumor assessments will be performed every 8 weeks starting from the date of first dose of study treatment, and as clinically indicated, until the first 12 months of treatment are completed or disease progression. If no progression, tumor assessments will occur every 12 weeks, and as clinically indicated until disease progression.
 
Every 28 days will be considered one cycle. Clinical visits will be twice per cycle for the 1st two cycles, then once per cycle from there on. The therapy on clinical trial will continue until disease progression (radiological), or intolerable adverse effects, or subject's wish to withdraw consent.
 
Follow up:
 
Subjects will be followed for safety until 30 days after study treatment discontinuation.
 
After treatment discontinuation for any reason other than progression, tumor assessments will continue every 8 weeks for up to 12 months after the first dose of study treatment.

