1.2.3.2.2 Everolimus in combination with endocrine therapy in HR+ breast cancer

The combination of everolimus with hormonal therapy has been assessed in different disease settings in HR+ breast cancer and showed evidence of efficacy of everolimus in this patient population ([Bachelot et al 2012; Baselga et al 2012; Piccart et al 2012](#)).

In newly diagnosed patients with ER+ breast cancer, a neoadjuvant randomized 270-patient Phase II study compared the combination of everolimus 10 mg QD and letrozole 2.5 mg QD to letrozole alone for 16 weeks of therapy prior to surgery. The overall response rate in the investigational everolimus + letrozole arm was higher than that with letrozole alone: 68% vs. 59% based on palpation ($p = 0.062$) and 58% vs. 47% based on ultrasound ($p = 0.021$) respectively, meeting the predetermined endpoint for efficacy. Additionally, there was a greater antiproliferative response in the investigational arm, with a decrease of the Ki67 proliferation index to <1 in 57% of patients in the everolimus arm compared to 30% of patients in the placebo arm ($p < 0.01$) ([Baselga 2009](#)). A randomized Phase III, double-blind, placebo-controlled study ([BOLERO-2 Study](#)) demonstrated very significant improvements in treatment of HR+ breast cancer that had recurred or progressed on letrozole or anastrozole. Response rate, progression-free survival (PFS), and clinical benefit rate were all significantly improved relative to exemestane monotherapy. The median PFS by local assessment was 7.8 months for everolimus + exemestane versus 3.2 months for exemestane ($HR = 0.45$; 95% CI: 0.38-0.54; $p < .0001$). Overall response rate (12.6% vs 1.7%; $p < .0001$) and clinical benefit rate (51.3% vs 26.4%; $p < .0001$) were superior in the everolimus + exemestane arm versus exemestane + placebo. Analyses by central assessment showed a median progression-free survival of 11 months with everolimus versus 4.1 months with placebo ($HR = 0.38$; 95% CI: 0.31 – 0.48; $p < .0001$) confirming the results of the primary PFS analysis ([Piccart 2012, Baselga 2012](#)).

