3.2 Objectives and related endpoints-phase II

Table 3-2 Objectives and related endpoints-phase II

	Objective	Endpoint
PHASE II		
Primary	Determine the Clinical Benefit Rate (CBR) at 24 weeks amongst patients receiving triple therapy with ribociclib + everolimus + exemestane, for advanced/metastatic HR+, HER2-negative breast cancer following progression on CDK 4/6 inhibitor.	Clinical Benefit Rate (CBR) defined as the proportion of patients with a complete (CR) or partial response (PR), or with stable disease (SD) at 24 weeks as per RECIST 1.1 or Non-CR Non-PD (NCRNPD) at week 24.
Secondary	To determine centrally assessed progression Free Survival (PFS) in HR+ HER2-negative advanced breast cancer.	Progression-free survival (PFS), defined as the time from date of treatment to the date of first documented progression or death due to any cause. If a

Objective	Endpoint
	subject has not had an event, PFS will be censored at the date of last adequate tumor assessment. Disease progression for primary efficacy endpoint derivation will be based on the central radiologist's tumor assessment.
To determine overall response rate (ORR)	Overall response rate (ORR) defined as the proportion of patients whose best overall response is either complete response (CR) or partial response (PR) according to RECIST 1.1.
To determine Overall Survival (OS)	This is defined as the time from treatment initiation with study treatment until death as a result of any cause.
To determine Duration of Overall Response (DOR)	Duration of Overall Response defined as the time between the initial response to the treatment with the combination of ribociclib+everolimus+ exemestane, and subsequent disease progression or recurrence.
To evaluate time to deterioration or ECOG performance status	Time to definitive deterioration of ECOG performance status from baseline.
To determine safety and tolerability	Adverse Events (AEs), serious AE (SAEs), changes in hematology and chemistry values, vital signs, dose interruptions, reductions and dose intensity.
To determine the PK profile of ribociclib and everolimus in the triplet combination	PK parameters including, but not limited to, AUC _{0-4h} , C _{trough} , C _{max} , accumulation ratio (Racc)

4 Study design

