7.1.7 Efficacy Follow-up

Patients enrolled in this study who discontinue study treatment for any reason other than disease progression will be followed up every 8 (± 1 weeks) weeks via a phone call and CT/MRI scans as detailed in [Table 7-1](#) and [Section 7.2](#), until disease progression or until 15 months after last patient enrolled into the study, whichever comes first. Antineoplastic therapies beginning during this F/U period must be recorded on the Antineoplastic Therapies Since Discontinuation of Study Drug eCRF.

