7.2 Assessment types

7.2.1 Efficacy assessments

7.2.1.1 Imaging tumor assessments

Tumor response will be assessed locally and centrally according to RECIST Version 1.1 ([Eisenhauer et al 2009](#)). The decision regarding patient management will remain with the local investigator. Patients should have at least one documented measurable lesion (per RECIST v1.1) or in the absence of measurable disease, have at least one lytic or mixed (blastic/lytic) bone lesion at study entry.

Imaging assessments will be performed at screening within 21 days prior to first dose of study treatment and subsequently every 8 weeks (± 1 week) from day one of study treatment during the first 12 months and every 12 weeks (± 2 weeks) thereafter. See [Table 7-2](#) for details of assessments. The 8-week (or 12 week) interval should be respected regardless of whether study treatment is temporarily withheld or modified.

After baseline, selected assessments should be performed on cycle 1 day 1 (will not need to be repeated on day of treatment if performed within 3 days of C1D1) see [Table 7-1](#).

If a patient discontinues treatment for reasons other than radiological documentation of progression of disease, an efficacy assessment should be performed at the time of End of Treatment unless a CT/MRI for tumor measurement was performed within 21 days. Efficacy

assessments should continue as per the scheduled visit per [Table 7-1](#) and [Table 7-2](#), [Table 7-3](#), and [Table 7-4](#).

To the extent possible, each lesion should be assessed using the same imaging method throughout the study.

All patients will undergo CT, PET CT or MRI of the chest, abdomen and pelvis at baseline and subsequent scheduled visits per [Table 7-2](#). The preferred imaging methodology is CT with intravenous (i.v.) contrast. However, if at baseline, a patient is known to have a contraindication to CT i.v. contrast media or develops a contraindication during the trial, a non-contrast CT or PET CT is allowed. MRI plus contrast is allowed, however not recommended of the chest due to respiratory artifacts.

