10.5 Objectives

10.5.1 Primary objectives

Phase I: The primary objective of this dose escalation part of the study is to estimate the MTD(s) and/or RP2D of ribociclib in combination with everolimus and exemestane in postmenopausal women with HR+ HER2- advanced breast cancer.

Phase II: The primary objective is to evaluate efficacy measured by Clinical benefit rate (CBR) at 24 weeks for the triple combination of ribociclib + everolimus + exemestane among patients with HR+HER2- advanced breast cancer following the progression of CDK 4/6 inhibitors.

Demonstration of significant Clinical Benefit Rate (CBR) will be based on this study with at least an 80% power to test the null hypothesis that the clinical benefit rate in 24 weeks is at least 10% or less with an alternative hypothesis that this rate is above 10%.

The Clinical benefit rate will be presented together with an exact 95% Clopper-Pearson confidence interval. The null hypothesis will be rejected and successful clinical benefit will be demonstrated if the lower limit of the 95% confidence interval is greater than at least 0.10. Thus, if 8 or more patients show clinical benefit at 24 weeks then the null hypothesis will be rejected and significant clinical benefit will be demonstrated. Primary efficacy analysis will be performed on the FAS. For primary efficacy variable, the analysis time point is when all patients who are enrolled complete 24 weeks or discontinue from the study earlier. Phase 1 patients who had received the RP2D and are post CDK 4/6 completing 24 weeks or discontinue early will also be included in the final phase II analysis.

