².=After the last adequate tumor assessment. "Date of next scheduled assessment" is defined in [Section 14.1.25](#).

³.=The rare exception to this is if the patient dies no later than the time of the second scheduled assessment as defined in the protocol in which case this is a PFS event at the date of death.

The primary analysis and the sensitivity analyses must be specified in the protocol. Clearly define if and why options (1) are not used for situations C, E and (if applicable) F.

Situations C (C1 and C2): Progression or death after one or more missing assessments: The primary analysis is usually using options (1) for situations C1 and C2, i.e.

- (C1) taking the actual progression or death date, in the case of only one missing assessment.
- (C2) censoring at the date of the last adequate assessment, in the case of two or more consecutive missing assessments.

In the case of two or missing assessments (situation C2), option (3) may be considered jointly with option (1) in situation C1 as sensitivity analysis. A variant of this sensitivity analysis consists of backdating the date of event to the next scheduled assessment as proposed with option (2) in situations C1 and C2.

Situation E: Treatment discontinuation due to 'Disease progression' without documented progression: By default, option (1) is used for situation E as patients without documented PD should be followed for progression after discontinuation of treatment. However, option (2) may be used as sensitivity analysis. If progression is claimed based on clinical deterioration instead of tumor assessment by e.g. CT-scan, option (2) may be used for indications with high early progression rate or difficulties to assess the tumor due to clinical deterioration.

Situation F: New cancer therapy given: the handling of this situation must be specified in detail in the protocol. However, option (1), i.e. censoring at last adequate assessment may be used as a default in this case.

Additional suggestions for sensitivity analyses

Other suggestions for additional sensitivity analyses may include analyses to check for potential bias in follow-up schedules for tumor assessments, e.g. by assigning the dates for censoring and events only at scheduled visit dates. The latter could be handled by replacing in [Table 14-7](#) the "Date of last adequate assessment" by the "Date of previous scheduled assessment (from baseline)", with the following definition:

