3.5.2.2 Phase II

- Clinical Benefit Rate (CBR):

Clinical Benefit Rate (CBR) is defined as the proportion of patients with a complete response (CR), partial response (PR), stable disease (SD) or Non-CR Non-PD (NCRNPD) at 24 weeks as per RECIST V1.1. Thus, any instance of CR, PR, SD or NCRNPD in the first 24 weeks of the treatment, without having an instance of progressive disease (PD) will be accounted for, while calculating CBR. The instances of unconfirmed CR and/or PR will also be accounted for, while calculating CBR.

Demonstration of significant Clinical Benefit Rate (CBR) will be based on this study with at least an 80% power to test the null hypothesis that the clinical benefit rate in 24 weeks is at least 10% or less with an alternative hypothesis that this rate is above 10%.

All the other patients will be counted as not having clinical benefit.

The study is designed to test the following statistical hypothesis:

$$H_0 : \text{CBR} \leq 10\% \text{ vs. } H_1 : \text{CBR} > 10\%$$

The null hypothesis will be rejected and successful clinical benefit will be demonstrated if the lower limit of the 95% confidence interval is greater than at least 0.10. Thus, if 8 or more patients show clinical benefit at 24 weeks then the null hypothesis will be rejected and significant clinical benefit will be demonstrated.

To show significant clinical benefit, currently at least ≥ 8 patients will have to achieve CBR at 24 weeks. But if the number of patients enrolled in the study is higher than the planned number of 33 patients (approximately 44 to 46), then the requirement for the number of patients to have achieved CBR will also increase (up to ≥ 10 patients).

CBR will be summarized by frequency and percentage together with the 95% confidence intervals. An exact binomial confidence interval (implemented using SAS procedure FREQ with EXACT statement for one-way tables) will be calculated [Clopper & Pearson, 1934].

CBR will be calculated based on FAS; however, patients with only non-measurable disease at baseline will be included in the numerator if they achieved a complete response.

For primary efficacy variable, the analysis time point is when all patients who are enrolled complete 24 weeks or discontinue from the study earlier. Phase 1 patients who had received the RP2D and are post CDK 4/6 completing 24 weeks or discontinue early will also be included in the final phase II analysis.

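### SAP scoring can credit clinical benefit to patients who stopped early for investigator-called progression without central PD, and central PFS censors them

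*Protocol*

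**What the plan says.** **Follow-up imaging.** The Synopsis (Study design, Follow up) states: "After treatment discontinuation for any reason other than progression, tumor assessments will continue every 8 weeks". Protocol 7.1.7 has the same limit: "Patients enrolled in this study who discontinue study treatment for any reason other than disease progression will be followed up". Section 4.1.3 agrees. Table 7-2 runs scans until disease progression without saying whose reading counts.

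**Who decides.** Protocol 7.2.1.1: "The decision regarding patient management will remain with the local investigator". Scans go to the imaging CRO within two weeks, but no section makes central confirmation of PD a condition for stopping treatment or imaging.

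**Which read is analysed.** Protocol Table 3-2: "Disease progression for primary efficacy endpoint derivation will be based on the central radiologist's tumor assessment". SAP 3.5.2.2 and 3.7.2.2 also base the primary CBR and the main PFS analysis on central assessments. PFS without an event is censored at the last adequate assessment.

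**How CBR is counted.** Protocol Table 3-2 asks for CR, PR, SD or non-CR/non-PD at week 24. SAP 3.5.2.2 instead credits "any instance of CR, PR, SD or NCRNPD in the first 24 weeks of the treatment, without having an instance of progressive disease (PD"). SAP 3.7.2.1 uses the same rule for Phase I. SAP section 5 lists no change to the protocol's analyses, and SAP 3.5.3 marks missing values and discontinuations for the primary endpoint as not applicable.

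**Planned checks.** CBR and PFS are repeated on local reads. Central and local agreement is tabulated, with kappa, for best response only.

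**The concern.** Imaging is ended by one reader and the endpoint is scored by another. When the investigator sees progression and the central reader does not, the patient can leave with no later scan on which the central reader could record PD.

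For CBR, the SAP rule treats that absence of central PD as success once there has been one earlier central SD. Each group is judged against a fixed 10% benchmark with no control arm, so nothing offsets wrongly credited patients, and the threshold is only 8 of 33 or up to 10 of about 46.

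For PFS, the patients censored in this way are those the investigator judged to be progressing, so the censoring is unlikely to be independent of prognosis.

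**Working it through.** **1. One patient under each rule.** Central SD at week 8. At week 16 the scan is PD locally and SD centrally, treatment stops for progression, and no further scan is taken.

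| Rule | Result |
|---|---|
| Protocol Table 3-2, status at week 24 | No week-24 assessment: not clinical benefit |
| SAP 3.5.2.2, any instance without PD | Central SD and no central PD: clinical benefit |
| SAP 3.7.2.2, central PFS | Censored at week 16 |
| SAP 3.7.2.2, local-read PFS | Event at week 16 |

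Later events may not enter central PFS either. By the defaults in protocol Table 14-7, new anticancer therapy censors at the last adequate assessment, and so does a death after two or more missed assessments.

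**2. The plan's own figure.** Inputs: the null, which protocol 10.5.1 words as "the clinical benefit rate in 24 weeks is at least 10% or less" and which is used here as p = 0.10; alternative p = 0.30; success at 8 or more of 33 (protocol 10.4.2). The exact binomial gives:
- P(X ≥ 8 | n = 33, p = 0.30) = 0.818, which reproduces the stated 80% power.
- P(X ≥ 8 | n = 33, p = 0.10) = 0.0141.

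SAP section 4 reports 46 patients recruited to Group 1, and SAP 3.5.2.2 raises the threshold to as many as 10 at that size: P(X ≥ 10 | n = 46, p = 0.10) = 0.0140.

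**3. Effect of crediting some non-benefit patients.** Let q be the share of truly non-benefit patients whom the SAP rule credits by this route. The documents do not give q, so the values are assumptions. The apparent rate is p' = 0.10 + 0.90q.

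| q | p' | P(≥ 8 of 33) | P(≥ 10 of 46) |
|---|---|---|---|
| 0 | 0.100 | 1.4% | 1.4% |
| 2.5% | 0.1225 | 4.2% | 4.9% |
| 5% | 0.145 | 9.5% | 12% |
| 10% | 0.190 | 28% | 37% |

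In patients, q = 5% is 0.05 × 0.90 × 33 ≈ 1.5 in a group of 33, or 0.05 × 0.90 × 46 ≈ 2.1 in a group of 46.

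**4. PFS, direction and upper limit only.** Assume a constant hazard and that a fraction f of local PDs is not PD centrally and is censored there, with no discordance the other way. The central hazard is then (1 − f) times the local one, and the median is longer by at most 1/(1 − f): 1.11, 1.25 and 1.43 for f = 10%, 20% and 30%.

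**The case against.** **The protocol definition already excludes these patients.** This stands. Under Table 3-2 there is no upward bias in CBR. A reader might infer that the primary CBR is inflated under either definition; the documents support that only for the SAP rule.

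**Not every non-benefit patient is exposed.** This stands. Deaths, dropouts without an evaluable scan and patients with unknown response are not credited, and central SD on the week-24 scan itself is genuine benefit by definition. Setting q equal to the whole local/central discordance rate would overstate the effect.

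**PFS discordance runs both ways.** This stands. Central PD before local PD is also an event. With a 24-week median the chance of progression per 8-week interval is 1 − 0.5^(8/24) = 0.206. Lengthening from f = 10% or 20% would be cancelled if central review called PD first on 0.206f/0.794 = 2.6% or 5.2% of locally non-PD scans.

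**Local-read repeats are planned.** They would show the gap, but they leave the primary central CBR and the central PFS as they are.

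**The stopping of scans is inferred.** No sentence says that a local PD ends imaging; it follows from 7.1.7 and 7.2.1.1 read together. SAP 3.5.2.2 also describes the central responses as supplied by the investigator, which leaves the deciding reader unclear. Neither point removes the gap, since nothing requires central confirmation.

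**Two further inferences fail.** Situation E of Table 14-7, with its premise that "patients without documented PD should be followed for progression after discontinuation of treatment", might seem contradicted by the follow-up rule. But it concerns clinical progression without documented PD, and 7.2.1.1 keeps scanning patients who stop without radiological progression. The earlier doublet trial's local median of 7.8 months might be set against "Analyses by central assessment showed a median progression-free survival of 11 months with everolimus", but its scan-stopping rule is not given, so the difference says nothing about this mechanism.

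**Conclusion.** The point holds in a limited form. The SAP's CBR rule departs from the protocol's week-24 definition without declaring it, and one consequence is that patients taken off treatment for investigator-assessed progression before week 24, without central PD, can count as successes. With a true CBR of 10%, crediting 2.5% to 10% of non-benefit patients would raise false success from 1.4% to between 4.2% and 28% (33 patients, at least 8) or between 4.9% and 37% (46 patients, at least 10). These shares are assumptions, and the actual effect cannot be derived from the documents.

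For central PFS, censoring at the last adequate scan is likely to be informative and tends to lengthen the estimate. The factors of 1.11 to 1.43 are upper limits under one-directional discordance. A reader might take them as expected bias, but without data on discordance in both directions the documents do not support that.

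**What to change.** 1. **SAP 3.5.2.2 and 3.7.2.1.** Define clinical benefit as centrally assessed CR, PR, SD or non-CR/non-PD in the Week 24 window of SAP Table 3-4 (after day 142, up to day 198), with no earlier PD. Count every patient without an evaluable Week 24 assessment as no clinical benefit, including those who stopped earlier for investigator-assessed progression. This restores the Table 3-2 definition.
2. **SAP 3.7.2.2.** Add a sensitivity analysis of central PFS in which investigator-assessed PD with no later central assessment is an event on that date. Tabulate local against central agreement in PD status and PD date, beside the planned kappa for best response.

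**Cost.** Both are SAP wording and use data already collected. CBR becomes slightly less favourable. The PFS sensitivity analysis overlaps with the planned local-read PFS, so it adds little work.

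Extending scans until central confirmation is not proposed. It needs additional imaging, the 79 Phase II patients (46 + 33) were already enrolled, and scans after new anticancer therapy would not enter central PFS under the Table 14-7 default.
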